STUDY PROTOCOL – COVER PAGE
Official Title:	
Acute Effects of Combined and Isolated Caffeine and Theanine Supplementation on Physical and Cognitive Performance in Competitive Athletes: A Randomized, Double-Blind, Placebo-Controlled Crossover Study	
Sponsor-Investigator:	
Assoc. [name] [name]	
Faculty of Sport Sciences, Sinop University, Türkiye	
[contact]	
Ethics Committee Approval:	
Sinop University Human Research's Ethics Committee	
Approval Number: 2025/337	
Approval Date: 22 May 2025	
Document Type:	
Study Protocol	
Version and Date:	
Version 1.0 – October 21, 2025	
Funding Source:	
Self-supported academic research	

Method

Study Design

This study employed a randomized, double-blind, placebo-controlled, crossover design to examine the effects of caffeine (CAF), theanine (THE), their combination (COM), and a placebo (CON) on physical and cognitive performance in young, healthy, competitive athletes. Each participant completed all four experimental conditions in a randomized order, with a washout period of at least 72 hours between sessions to minimize potential carryover effects. The randomization sequence was generated by an independent researcher using a computer-based randomization tool (Urbaniak & Plous, 2013). To ensure familiarity and minimize learning effects, all participants completed a familiarization session one week prior to the experimental trials. Physical and cognitive performance were assessed across multiple primary outcomes, including maximal strength, intermittent aerobic endurance, and eye-hand coordination. All procedures were conducted in accordance with the of Helsinki. The study protocol was approved by the Sinop University Human Research's Ethics Committee (Approval No: 2025/337), and all participants provided written informed consent prior to participation.

Participants

12 males and 8 females athletes $(19.9 \pm 2.4 \text{ years}; 167.3 \pm 7.6 \text{ cm} \text{ height}; 63.5 \pm 10.2 \text{ kg} \text{ body mass}; 27.5 \pm 6.7 \text{ kg} \text{ lean body mass}; 22.6 \pm 8.2\% \text{ body fat}; 22.6 \pm 2.3 \text{ kg·m}^{-2} \text{ BMI})$ from both team and individual sports were recruited for the study (Table 1). During the first laboratory visit, anthropometric and body composition assessments were performed to characterize the participant sample. Standing height and body mass were measured to the nearest 0.1 cm and 0.1 kg using a calibrated stadiometer and digital scale (Seca, Hamburg, Germany). Body composition was determined via multi-frequency bioelectrical impedance analysis (InBody 770; InBody Co., Seoul, South Korea). All measurements were conducted in the morning, with participants wearing light clothing and having abstained from exercise, food, and caffeine for at least 3 hours prior to testing.

Inclusion criteria were: (i) active participation in individual or team sports at a competitive level, (ii) age between [insert range, e.g., 18-30] years, and (iii) absence of any known medical or metabolic disorder. Exclusion criteria included: (i) history of cardiovascular, neurological, or musculoskeletal disorders within the past 12 months, (ii) known intolerance or hypersensitivity to caffeine or theanine, (iii) allergy to mannitol or other excipients used in capsule formulation, (iv) current use of prescription medications, and (v) physician-directed restriction of caffeine or theanine consumption.

[figure not shown]

Figure 1. Flowchart

The required sample size was estimated using an a priori power analysis (G*Power 3.1.9.7; Düsseldorf, Germany) for a repeated-measures ANOVA with four conditions (CAF, THE, CAF + THE, CON), assuming a moderate effect size (f = 0.25), $\alpha = 0.05$, and statistical power ($1 - \beta$) = 0.80. The analysis indicated a minimum required sample of 16 participants. To account for potential attrition or missing data, 20 athletes were recruited; all completed the study protocol.

Supplementation Protocol

Capsules were ingested 60 minutes prior to testing to allow sufficient time for peak plasma caffeine concentrations (Pallares et al., 2013). The supplementation conditions were structured as follows: caffeine (CAF, 3 mg/kg⁻¹ anhydrous caffeine), theanine (THE, 200 mg L-theanine), combined caffeine and theanine (COM, 3 mg/kg⁻¹ caffeine + 200 mg theanine), and placebo (CON, mannitol). Caffeine capsules contained anhydrous caffeine powder (Oxford brand pure caffeine powder; ISO 14001 certified; 98.5% purity; The Oxford Vitality Health Company Ltd., London, UK), and theanine capsules contained pure L-theanine powder Ocean (L-Theanine, 200 mg; Orzax Pharmaceuticals, Istanbul, Turkey; active ingredient manufactured in Germany). Placebo capsules contained mannitol, a non-nutritive sugar alcohol with no known ergogenic or ergolytic properties (Flueck et al., 2016). All supplements were administered in visually identical gelatin capsules to ensure blinding across conditions. Each participant ingested the same number of capsules (five in total) in all conditions to maintain consistency in capsule count and total mass. Neither participants nor researchers could distinguish between conditions due to the capsules' identical appearance, texture, and color.

Participants were instructed to refrain from alcohol consumption and strenuous exercise for 24 hours before each trial and to abstain from any dietary supplements throughout the study period. They maintained 24-hour dietary records for the day preceding each test and a weekly log of their habitual caffeine intake. To standardize pre-trial nutritional status, participants replicated their recorded dietary intake and hydration patterns before each visit. To preserve ecological validity and reduce potential caffeine withdrawal effects, participants were permitted and encouraged to maintain their usual daily caffeine consumption during the study period, as recommended by Tallis et al. (2021) and Pickering & Kiely (2019).

Data Collection Tools

All sessions were conducted under standardized computer laboratory and indoor sports hall conditions. The eye-hand coordination assessment was conducted in a quiet, temperature-controlled laboratory using a desktop computer system. Ambient conditions were maintained at approximately 22 ± 1 °C and $50 \pm 5\%$ relative humidity. All other performance tests (strength and aerobic endurance) were carried out in an indoor sports hall under comparable conditions (temperature 21-23 °C, relative humidity 45–55%). Environmental parameters were monitored at the start of each session using a calibrated digital room thermo-hygrometer. Lighting, background noise, and testing times were standardized across all trials to ensure intraindividual consistency.

Testing sessions were held in the morning at 09:00 a.m. to minimize the potential effects of circadian variation and diurnal performance fluctuations. The sequence of tests was standardized as follows: eye-hand coordination, maximal strength, and aerobic endurance. Adequate rest intervals were provided between tests to prevent fatigue and carry-over effects. The following measurements were collected during each experimental condition:

Strength Tests

Maximal isometric strength was assessed using a Lafayette digital dynamometer (Takei Scientific Instruments Co. Ltd, Tokyo, Japan) to measure handgrip, back, and leg strength. The device was checked for calibration prior to each testing session according to the manufacturer's recommendations.

Participants performed three maximal voluntary contractions for each test, with at least 60 seconds of rest between attempts to minimize fatigue. Handgrip strength was assessed with participants seated, shoulders adducted, elbows flexed at 90°, and the dynamometer handle adjusted to individual hand size. Back strength was measured in a standing position with the participant pulling upward on a handle attached to the dynamometer's base platform while maintaining a neutral spine. Leg strength was evaluated in a similar posture, with participants exerting maximal upward force through a chain-linked platform while keeping their knees slightly flexed.

The mean of the three trials for each test was recorded as the participant's strength score, expressed in kilogram-force (kgf) as displayed by the device. All strength assessments were performed in accordance with the standardized procedures for isometric testing recommended by the American College of Sports Medicine (ACSM, 2021). American College of Sports Medicine. (2021). ACSM's Guidelines for Exercise Testing and Prescription (11th ed.). Wolters Kluwer.

Aerobic Endurance

Aerobic endurance was assessed using the Yo-Yo Intermittent Endurance Test Level 1 (Yo-Yo IET-1), which evaluates participants' ability to perform repeated bouts of exercise with brief recovery periods. The protocol followed the standardized procedures described by Bangsbo et al. (1996). Testing was performed on a flat, non-slip indoor surface with two parallel lines marked 20 m apart and a recovery line placed 5 m behind the starting line. Prior to testing, participants completed a standardized 5-minute dynamic warm-up consisting of jogging and mobility drills. Bangsbo, J. (1996).

Participants ran back and forth between the 20-m lines in time with audio cues from the official Yo-Yo IET Level 1 recording, with running speed progressively increasing throughout the test. After each 2×20 m shuttle, a 5-second active recovery period was provided, during which participants jogged to and from the recovery line. The test was terminated when a participant failed to reach the 20-m line on two consecutive occasions, and the total distance covered (m) was recorded to the nearest meter as the performance outcome.

Eye-Hand Coordination

Eye-Hand Coordination Test (Multidirectional and Unpredictable Direction) was used to evaluate participants' ability to perform accurate, continuous manual motor actions based on dynamic visual processing. The test was administered in a quiet, temperature-controlled laboratory (22 ± 1 °C; relative humidity $50 \pm 5\%$) using CogniFit's proprietary digital platform (CogniFit Inc., New York, USA) on a desktop computer.

They were instructed to remain seated comfortably, maintain a neutral wrist position, and use their dominant hand for all trials. During testing, participants tracked a small moving circle ("ball") that followed an unpredictable multidirectional trajectory. The task required maintaining a cursor (crosshair) within the moving circle as precisely as possible. Visual feedback was provided continuously: green when on-target, orange when near the boundary, and red when the cursor left the target area. Each assessment included two initial learning segments (7 s slow + 7 s fast) followed by twelve testing segments alternating between slow (\approx 5 cm/s) and fast (\approx 10 cm/s) movement speeds, each lasting either 2333 ms (short) or 7000 ms (long), for a total duration of approximately 5-7 minutes including instructions. Prior to the main test, participants completed a brief familiarization session that included standardized on-screen practice trials lasting approximately 1 minute to minimize learning effects. Optional 10-15 second rest intervals were allowed between trials to avoid fatigue.

The following performance metrics were recorded automatically by the CogniFit software:

Accuracy (%): Percentage of time the cursor remained inside the circle (0–100; higher = better).

Accuracy - Fast Speed (%): Accuracy during fast segments (≥ 10 cm/s).

Accuracy - Slow Speed (%): Accuracy during slow segments (≤ 5 cm/s).

Accuracy - Long Segments (%): Accuracy during 7000 ms segments (sustained tracking).

Accuracy - Short Segments (%): Accuracy during 2333 ms segments (brief tracking).

Distance from Circle Center (pixels): Mean pixel distance between cursor and target center (0–1200; lower = better precision)

Performance scores were automatically normalized against CogniFit's age- and sex-matched normative database (percentile 0–100), following the developer's validity index ranges and completion-time criteria (54–58 s valid window). All assessments adhered to the manufacturer's standardized task protocol and validity thresholds (CogniFit Inc., 2023).

Statistical Analysis

The normality of the data set was initially evaluated using the Shapiro-Wilk test. Subsequently, the assumption of sphericity was examined through Mauchly's test, with the Greenhouse-Geisser correction applied in cases where sphericity was violated. Differences in strength, aerobic endurance, and eye-hand coordination outcomes across the four supplementation conditions (CAF, THE, COM, and CON) were analysed using a one-way repeated-measures analysis of variance (ANOVA). When significant main effects were observed, Bonferroni-adjusted pairwise comparisons were conducted to identify specific between-condition differences. The magnitude of effects was quantified using partial eta squared (ηp^2), interpreted as small (0.10–0.24), moderate (0.25–0.39), or large (\geq 0.40). For pairwise comparisons, Cohen's d for repeated measures and corresponding 95% confidence intervals (CI95%) were reported and interpreted as trivial (<0.20), small (0.20–0.49), moderate (0.50–0.79), or large (\geq 0.80) (Cohen, 1992). All statistical analyses were performed using IBM SPSS Statistics version 30.0 (IBM Corp., Armonk, NY, USA) and statistical significance was accepted at $\alpha = 0.05$ (two-tailed). Graphical visualizations were generated with GraphPad Prism version 10.0 (GraphPad Software, San Diego, CA, USA).

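### Several primary outcomes are each tested at 0.05 with no error control across them, and no primary score is named within strength or coordination

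*Combined protocol and SAP*

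**What the plan says.** The Study Design section sets the status of the outcomes: "Physical and cognitive performance were assessed across multiple primary outcomes, including maximal strength, intermittent aerobic endurance, and eye-hand coordination". These are domains rather than scores, the list is open-ended, and no order of importance is given.

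The measurement sections define the scores:

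- **Strength (three).** A dynamometer is used "to measure handgrip, back, and leg strength". Each test is scored as the average of its three attempts. There is no composite.
- **Endurance (one).** For the Yo-Yo test, "the total distance covered (m) was recorded to the nearest meter as the performance outcome".
- **Coordination (six).** The list opens with "The following performance metrics were recorded automatically by the CogniFit software" and gives overall accuracy, accuracy in fast, slow, long and short segments, and distance from the circle centre. The section adds "Performance scores were automatically normalized against" a normative database, without saying whether raw or normalised values are analysed.

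The Statistical Analysis section compares "Differences in strength, aerobic endurance, and eye-hand coordination outcomes across the four supplementation conditions" by one-way repeated-measures ANOVA, with two-tailed significance at 0.05. The one multiplicity provision is: "When significant main effects were observed, Bonferroni-adjusted pairwise comparisons were conducted to identify specific between-condition differences". The sample-size paragraph under Participants gives a calculation "for a repeated-measures ANOVA with four conditions", with f = 0.25, alpha 0.05 and power 0.80. It does not say which outcome this concerns.

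**The concern.** The Bonferroni step acts among the six condition pairs of one outcome, and only after that outcome's own F test has passed at 0.05. Nothing acts across outcomes: there is no alpha split, hierarchy, gatekeeping, or rule on how many outcomes must be significant for a claim. With several primary outcomes, the chance of at least one false-positive ANOVA therefore exceeds 0.05.

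Reading the three domains as separate questions clears only endurance. A strength claim could rest on any of three scores and a coordination claim on any of six. One significant score among several could not then be told from chance at the level a reader would assume. All 20 athletes have completed the study, so a score named as primary now could be chosen with the results in view unless an earlier dated record fixes it.

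**Working it through.** **1. The plan's own figure.** The stated inputs are m = 4 conditions, f = 0.25, alpha 0.05, power 0.80 and a minimum of N = 16. The correlation among repeated measures (rho) and the sphericity factor (eps) are not given. With eps = 1, the noncentral F calculation uses lambda = f²·N·m/(1 − rho), with df 3 and 3(N − 1).

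- At rho = 0.675: lambda = 0.0625 × 16 × 4/0.325 = 12.31, power 0.81. N = 15 gives 0.78, so 16 is the minimum.
- At rho = 0.5: lambda = 4/0.5 = 8, power 0.61, and 24 participants would be needed.

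So 16 is attainable for one ANOVA at 0.05 if rho is about 0.66-0.69.

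**2. False-positive omnibus tests with one score per domain.** If the three are independent, 1 − 0.95³ = 0.143. Simulated null trials (100,000 per setting, 20 participants, four conditions, sphericity) with between-outcome correlation 0.3 / 0.5 / 0.7 / 0.9 give 0.138 / 0.130 / 0.113 / 0.088.

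**3. All ten scores.** The accuracy scores overlap by construction, so independence is not a usable model. They were built from four speed-by-length cells weighted by 7000 and 2333 ms. Six long and six short segments were assumed: 6 × 7.000 + 6 × 2.333 = 56.0 s. This is the only split of twelve inside the 54-58 s validity window, if that window covers testing segments only. Distance was assumed correlated −0.85 with overall accuracy. The chance of at least one false-positive omnibus test is:

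| Within-domain correlation | 0.3 | 0.5 | 0.7 |
|---|---|---|---|
| Ten scores, domains independent | 0.313 | 0.286 | 0.262 |
| Ten scores, shared cross-domain component 0.3 | 0.271 | 0.255 | 0.233 |
| Strength alone, domains independent | 0.140 | 0.127 | 0.114 |
| Coordination alone, domains independent | 0.158 | 0.140 | 0.122 |

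At within-domain correlation 0.9 the figures are 0.21-0.22 for ten scores, 0.09 for strength and 0.10 for coordination. An intermediate family of five (three strength scores, Yo-Yo distance, overall accuracy) gives 0.17-0.22 over the same range.

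**4. What Holm on the omnibus tests achieves.** Under the global null, the chance of any omnibus rejection is at most about 0.05 (0.03-0.04 for ten overlapping scores). This does not carry over to pairwise claims. When some conditions truly differ, many scores pass the gate and each then spends its own 0.05 on pairs. Simulation at between-outcome correlation 0 to 0.5, with either CAF = COM above THE = CON or one condition differing, gives these chances of a false pairwise claim:

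- Omnibus-only Holm: 0.04-0.07 (three scores), 0.12-0.21 (ten).
- Holm over all pairs of all primary scores: at most about 0.05.

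**5. Power at n = 20.** At rho = 0.675, lambda = 0.0625 × 20 × 4/0.325 = 15.38. Omnibus power for a single true effect of f = 0.25 is:

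| Assumed rho | alpha 0.05 | 0.05/3 = 0.0167 | 0.05/10 = 0.005 |
|---|---|---|---|
| 0.66-0.69 | 0.89-0.92 | 0.78-0.82 | 0.63-0.69 |
| 0.5 | 0.73 | 0.56 | 0.39 |

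For pairs, take rho 0.675 and CAF = COM above THE = CON at f = 0.25 on every score. The two levels differ by 0.5 SD and the SD of a paired difference is √(2 × 0.325) = 0.806. Power per truly different pair is 0.45 with Bonferroni within a score, and 0.33 (three scores) or 0.18 (ten) with Holm over all pairs.

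**The case against.** **The plan never promises 5% across outcomes.** This stands. The Statistical Analysis section sets a per-test level, so the figures above compare a family-wise rate with a per-test 0.05. They do not show a broken promise. Whether three domains form one family is partly judgement, and endurance taken alone does hold 0.05. But the plan calls the outcomes primary and gives no rule for combining them, and within strength and coordination the excess remains even if the domains are separated.

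**Bonferroni is already used.** It is, but only among conditions within a score, after an unadjusted F test.

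**The correlations are guesses.** They are, including the −0.85 for distance, which has no source in the documents. The rate exceeded 0.05 at every correlation tried. Ten is not a firm upper limit either: the plan does not say whether one or both hands are tested, and the outcome list is open-ended.

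**Holm on the omnibus tests does not protect the pairwise claims.** This is right, and the study's questions are largely pairwise. The wording of the fix must therefore limit what the 0.05 covers.

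A reader might go further than the documents allow in three ways:

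- Treating ten scores as independent gives 1 − 0.95¹⁰ = 0.40. The accuracy scores share segments, so that figure does not apply.
- One might infer that the sample size of 16 is wrong. It cannot be checked without rho, and it is attainable.
- One might infer that primary scores were picked after the results. The documents show only that nothing in them would prevent it.

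**Conclusion.** The point holds. As written, the plan gives a chance of at least one false-positive primary ANOVA of about 0.09-0.14 with one score per domain (correlation 0.9 to 0) and roughly 0.2-0.3 if all ten overlapping scores count, with each test at 0.05. These figures rest on assumed between-outcome correlations, the assumed overlap structure, sphericity and n = 20. The direction depends on none of the correlation values tried. The absence of a named primary score within strength and coordination rests on the text alone.

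It would be too much to say that Holm on the omnibus tests brings every claim to 0.05: that holds for whether condition affects a score, not for which conditions differ.

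**What to change.** **Statistical Analysis section.** List the primary scores and say whether coordination values are raw or normalised. Use one score per domain if a record dated before the data were seen names it (for example the ethics application or a saved power calculation), and label the rest secondary. Otherwise put all analysed scores in the primary family. Then add:

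> The omnibus F tests of all primary scores are adjusted by the Holm method, so the family-wise 0.05 applies to the claim that condition affects a score. Pairwise comparisons are run only for scores that remain significant, and their Bonferroni adjustment holds within a score, not across scores. This adjustment was added after data collection was complete.

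If a family-wise 0.05 is also to be claimed for pairwise differences, apply Holm to all pairwise p-values of all primary scores together. Otherwise do not make that claim.

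**Sample-size paragraph under Participants.** State that the 0.80 power refers to one ANOVA at unadjusted 0.05, name the outcome if a record shows it, and say that power at the adjusted level is lower.

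**Cost.** A few sentences and recalculated p-values. The sample is fixed at 20, so the loss of power shown in step 5 cannot be recovered by recruitment. It is modest for three scores if rho is near 0.675, and substantial for ten scores, for a lower rho, or if Holm covers all pairs. The omnibus losses are for a single true effect at the strictest Holm step, and are smaller if several effects are real.

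### The four-session crossover is analysed on condition alone: session drift left after familiarisation would widen intervals, cost power and shrink the reported effect sizes, without biasing the mean contrasts on average

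*Combined protocol and SAP*

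**What the plan says.** Study Design: "Each participant completed all four experimental conditions in a randomized order". On how the orders were produced: "The randomization sequence was generated by an independent researcher using a computer-based randomization tool". It does not say whether conditions were balanced over the four sessions.

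The document treats learning as a risk and acts on it. Study Design: "To ensure familiarity and minimize learning effects, all participants completed a familiarization session". The Eye-Hand Coordination section adds "standardized on-screen practice trials lasting approximately 1 minute to minimize learning effects". Other sources of session-to-session change are also controlled. Supplementation Protocol: "participants replicated their recorded dietary intake and hydration patterns before each visit". Data Collection Tools: "Lighting, background noise, and testing times were standardized across all trials to ensure intraindividual consistency".

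The analysis in the Statistical Analysis section has one factor: outcomes "across the four supplementation conditions (CAF, THE, COM, and CON) were analysed using a one-way repeated-measures analysis of variance". A Greenhouse-Geisser correction follows if Mauchly's test is significant, and Bonferroni pairwise comparisons follow a significant main effect. Partial eta squared, and Cohen's d with 95% intervals, are to be reported. No session, period or sequence term appears anywhere.

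Participants: "To account for potential attrition or missing data, 20 athletes were recruited; all completed the study protocol".

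**The concern.** Each athlete repeats the same tracking task, maximal pulls and intermittent run in four sessions. Familiarisation and standardisation make large drift less likely, but they cannot exclude some learning or training gain from session 1 to session 4. If any remains, the planned model has nowhere to put it except the error term. Every F test is then less powerful and every interval wider than the same data could give. The effect sizes, which are reported results in their own right, come out smaller because their denominators contain drift.

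**Working it through.** **Inputs from the document.** n = 20 completers, m = 4 conditions, f = 0.25, two-sided alpha 0.05, target power 0.80, stated minimum N = 16.

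**Assumptions, because the document gives no value.** Within-athlete correlation ρ (0.7, with 0.5 as a check); session effects s1 to s4 in units of the total SD; condition means at ±0.25 SD, two up and two down, which gives f = 0.25.

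**1. The plan's own figure.** For a within-subject factor, λ = n·m·f²/(1 − ρ) on 3 and 3(n − 1) df. The stated 16 cannot be confirmed, because ρ is not stated. ρ = 0.67–0.68 gives exactly 16 (power 0.81 at n = 16, ρ = 0.67), ρ = 0.7 gives 15 and ρ = 0.5 gives 24. A value near 0.7 therefore fits the plan better than 0.5. The point does not depend on the 16.

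**2. What drift does to the error term.** With independent random orders, the expected error variance is (1 − ρ) + V. V is the variance of s1 to s4 with divisor 3. For linear drift δ per session, V = δ²(1.5² + 0.5² + 0.5² + 1.5²)/3 = (5/3)δ². The noncentrality becomes λ = 20·4·0.0625/(1 − ρ + V) = 5/(1 − ρ + V). At ρ = 0.7:

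| Session effects | V | Error variance | SE ratio | λ | Power by formula, F(3,57) | Simulated, as planned | Simulated, session added |
|---|---|---|---|---|---|---|---|
| none | 0 | 0.300 | 1.00 | 16.67 | 0.927 | 0.925 | 0.909 |
| linear 0.1 | 0.0167 | 0.317 | 1.03 | 15.79 | 0.912 | 0.910 | 0.909 |
| linear 0.2 | 0.0667 | 0.367 | 1.11 | 13.64 | 0.863 | 0.860 | 0.909 |
| linear 0.3 | 0.1500 | 0.450 | 1.22 | 11.11 | 0.778 | 0.772 | 0.909 |
| 0, 0.2, 0.3, 0.35 | 0.0240 | 0.324 | 1.04 | 15.43 | 0.905 | 0.906 | 0.910 |
| 0, 0.3, 0.45, 0.525 | 0.0539 | 0.354 | 1.09 | 14.13 | 0.876 | 0.876 | 0.910 |

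The linear rows used 20,000 simulated trials each (Monte Carlo SE at most 0.35 points), with the Mauchly/Greenhouse-Geisser rule in both models. The levelling rows used 4,000 to 8,000 trials. Independent repeats of 4,000 to 8,000 trials gave 0.86 vs 0.90–0.92 at linear 0.2 and 0.77–0.78 vs 0.90–0.91 at 0.3.

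At ρ = 0.5 (random orders, linear drift), power is 0.726 vs 0.697 with no drift and 0.596 vs 0.697 at drift 0.3. It is below 0.80 either way.

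**3. Type I error.**
- Independent random orders, ρ = 0.7: 5.0–5.3% as planned and 5.4% with session.
- Orders balanced over sessions (a 4 × 4 Williams square used five times): 4.2%, 2.4% and 0.8% as planned at linear drift 0.1, 0.2 and 0.3, against 5.0% with session.

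The mean condition contrast under the null is about zero at every drift.

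**4. Interval width.** For the pairwise 95% intervals, the width with session relative to the plan, at ρ = 0.7 and drift 0, 0.1, 0.2 and 0.3, is:
- random orders: 1.03, 1.01, 0.93, 0.84;
- balanced orders: 1.01, 0.98, 0.91, 0.82.

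**5. Effect sizes.** Take d as the mean over the SD of the paired difference, for conditions 0.5 SD apart. The approximate value is 0.5/√(2 × error variance):
- no drift: 0.5/√0.600 = 0.65;
- linear 0.2: 0.5/√0.733 = 0.58;
- linear 0.3: 0.5/√0.900 = 0.53.

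The simulated mean d is slightly higher, as sample d is in small samples: 0.67, 0.61 and 0.55–0.56. For partial eta squared, (3 + λ)/(60 + λ) gives 0.26, 0.23 and 0.20. The simulations gave 0.25, 0.22 and 0.20.

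**The case against.** The strongest case against is that no defect has been demonstrated. No drift is documented, several steps were taken to prevent it, and with no drift a session term costs power. A straight line with no levelling is also the least favourable shape: linear 0.3 means 0.9 SD from session 1 to session 4, after familiarisation. When learning slows, the gain nearly disappears. With one 0.2 step after session 1, the plan does slightly better (0.914 vs 0.905). At ρ = 0.7 the plan stays above its 0.80 target up to linear drift 0.2. All of this stands, and it limits the point to a conditional, minor one. It does not remove the point, because the cost is small and known, while the loss under sustained drift is larger.

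A reader might go further and infer that omitting session biases the comparison or makes the p-values invalid. The document does not support that. Order was randomised for each athlete, so a common session effect is independent of condition. Under simple randomisation a single realised list can be unbalanced and shift a contrast. At 0.5 within-athlete SD per session (0.5 × √0.3 = 0.27 total SD at ρ = 0.7), 95% of such shifts lie within 0.40 within-athlete SD. Conditional type I error then ranges from 0.01 to 0.15 (5th to 95th percentile of lists). Over lists it averages about 5%, because the enlarged error term already allows for that movement. Serious inflation would need all athletes to share one order, which is not what Study Design describes.

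The opposite shorthand, that only precision is affected, is also too strong. Cohen's d and partial eta squared are shrunk by drift on average.

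**Conclusion.** The point holds as a minor one. Condition is the only factor in a four-session design whose own text treats learning as a risk. With orders randomised within athlete, remaining drift leaves the mean contrasts unbiased and the F test's type I error near or below 5% on average. It widens intervals, lowers power and shrinks the standardised effect sizes.

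Under the assumptions above (ρ = 0.7, independent random orders), the session term gains about 5 power points at linear drift 0.2 and about 13–14 at 0.3. It gains under 1 point for 0, 0.2, 0.3, 0.35 and about 3 for first step 0.3 then halving. It gains nothing up to about linear 0.1. Direction does not depend on the assumed values; size does. The figures cover drift common to all athletes. Carryover that differs by condition is a separate question and is not assessed here.

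**What to change.** For each outcome, add session (1–4) as a fixed factor beside participant and condition.

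- **Condition test:** F from participant + session + condition, with the plan's Mauchly/Greenhouse-Geisser rule applied to the session-adjusted values (df 3ε and 54ε).
- **Contrasts and effect sizes:** take the Bonferroni-adjusted contrasts, 95% intervals, d and partial eta squared from session-adjusted estimates. Do not assume equal variances of the paired differences. An unstructured within-participant covariance with Kenward-Roger df is one way. A random participant effect alone is not enough: with one condition's within-athlete SD assumed two or three times the others, its type I error was 6.6% or 7.8%, against 5.2% or 5.1% under the Greenhouse-Geisser rule (random orders, no drift).
- **Reporting:** state this as a change to the planned analysis, and as post hoc if results have been seen. Show the planned ANOVA beside it. Say how the orders were generated, and give the 4 × 4 table of condition-by-session counts.

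**Cost.** No new data are needed: all 20 athletes completed, and session number is known from the randomisation sequence. Error df fall from 57 to 54 before ε. If there is no drift, random orders lose 1.6 power points at ρ = 0.7 and 2.9 at ρ = 0.5, and intervals are about 3% wider. Little of this comes from the lost df (by formula 0.927 on 57 df and 0.926 on 54 at ρ = 0.7). Most comes from chance imbalance of conditions over sessions, so balanced orders lose at most 0.3 points. Each outcome will also carry two analyses, which the write-up must keep distinct.
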